13.1.6. Exploratory Efficacy Analyses

13.1.6.1. Responder Analyses

The percentage of subjects with a decrease in ALP of $\geq 15\%$ and $\geq 40\%$ from Baseline will be summarized by treatment group. In addition, the percentage of subjects with ALP \leq ULN will be summarized by treatment group.

The percentage of subjects that meet the criteria of a responder based on each of the definitions below will be summarized by treatment group. The response classification at baseline will also be included in the summary:

- ALP $\leq 3x$ ULN and AST $\leq 2x$ ULN and total bilirubin \leq ULN (Corpechot 2008)
- ALP $\leq 1.5x$ ULN and AST $\leq 1.5x$ ULN and total bilirubin \leq ULN (Corpechot 2011)
- ALP $\leq 1.67x$ ULN and total bilirubin \leq ULN (Momah 2012)
- Normal bilirubin (values \leq ULN) and normal albumin (values \geq lower limit of normal) (Kuiper 2009)
- ALP $\leq 1.76 x$ ULN (Kumagi 2010)

Responder analyses will compare treatment groups using a Cochran–Mantel–Haenszel test stratified by the randomization stratification factor. Missing values will be considered as a non-responder.

13.1.7. Pharmacoeconomic and Health Outcomes Endpoints

Sufficient data will be collected on resource utilization and quality of life to undertake cost-effectiveness analyses that are relevant to the major countries taking part in this study. Resource utilization data on hospitalizations, healthcare provider visits, and medications will be combined with appropriate national unit costs to calculate a cost per patient per year in the study.

Quality of life data from patient-reported outcomes measures will be combined with survival data to calculate quality adjusted time in the study per patient. Cost-effectiveness analyses will report the incremental cost per major clinical outcome averted, liver-related death averted, life-year gained and quality-adjusted life year gained, including OCA as part of usual care versus usual care without OCA. Analyses will be conducted within the study and using a lifetime perspective. A separate economic analysis plan will be prepared and reported separately from this protocol.

13.1.8. Supportive Analysis

Per the International Conference on Harmonisation (ICH) E10 guidance, “where no obvious single optimal external control exists, it may be advisable to study multiple external controls”. In order to address the risks associated with the inclusion of a long-term placebo arm, supportive analyses of the primary endpoint will compare clinical outcomes in the OCA treatment arm to historical controls.

In an attempt to avoid the inherent biases with historical controls and to maintain the integrity of this comparison, one can invoke matching methods to optimize comparability and find a historical control that is “similar” to a participating subject. The historical database control

should be as similar as possible to the study population and should have been exposed to a similar standard of care (see [Section 5.5.2.2](#)).

A propensity score can be used to reduce bias through matching, stratification, regression adjustment, or some combination. Propensity scores use information from a pool of patients who do not participate in the study (historical controls) to identify what would have happened to participating subjects in the absence of the treatment. By comparing how outcomes differ for treated subjects relative to historical controls, it is possible to estimate the effects of the treatment.

Although it might be relatively simple to assign a historical control based on a single observable characteristic, in practice, if the matching process is to successfully mitigate potential bias, it has to be done considering a full range of covariates across which the treatment and historical controls might differ. Although the results of using matching controls are conditional only on the observed covariates, if one has the ability to measure many of the covariates that are believed to be related to the treatment assignment, then one can be fairly confident that approximately unbiased estimates for the treatment effect can be obtained. Both UK-PBC Group and the Global PBC Study Group formally collect numerous covariates that could be used for propensity score estimation including standard of care, eg, UDCA.

Historical controls will be chosen based on the same inclusion/exclusion criteria where possible.

Propensity scores will be estimated using the available covariates that predict receiving the treatment. Only covariates and not outcome variables will be included in the propensity score estimation. Therefore, there is no chance of biasing results in favor of one treatment.

The covariates and factors collected in the historical databases will be specified in the SAP.

Propensity scores will be estimated first through a logistic regression model with treatment group as the dependent variable and the above covariates/factors as independent variables. Then the stratum boundaries are determined based on the propensity score values for both groups (OCA population and control [historical and randomized placebo]) combined or in the OCA population or historical control group alone. Based on recommendations in the literature, quintiles of the estimated propensity score from the combined group will be used to determine the stratum boundary cut-offs for the different strata.

Outcome events collected in the historical database are: death (liver-related and all-cause), liver transplant, hepatocellular carcinoma, and other. Other is defined as cirrhosis or decompensation such as ascites, variceal bleed, and encephalopathy.

The propensity score quintile will be then be used as the stratification factor in the stratified log rank test to compare randomized OCA-treated subjects in the ITT population and historical controls (Overall Historical Control Population: both the UK-PBC Group and Global PBC Study Group databases) on the following outcomes:

- Time to death (all-cause)
- Time to liver-related death
- Time to liver transplant
- Time to liver transplant or death (all-cause)

- Time to liver transplant or liver-related death
- Time to hepatocellular carcinoma

KM estimates of the distribution of the time-to-event will be tabulated and graphed by treatment group. The tabulation will include the KM estimate of the medians and corresponding 95% CIs if the medians can be estimated. The number and percent of subjects censored and with events will be presented. The hazard ratio and 95% CI will be determined based on a Cox regression model stratified by randomization strata to estimate the magnitude of the effect.

Sensitivity analyses will be conducted limiting to the separate individual historical control databases, ie, UK-PBC Group and Global PBC Study Group. To evaluate the robustness of the propensity score estimations, additional algorithms and factors may be considered.

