13.1.9. Alternative Primary Analysis

Based on sample size re-estimations, it may be determined that subjects will be enrolled to receive open-label OCA from that point forward, and the new primary efficacy analysis will become the comparison of all subjects in OCA population, to all control subjects (randomized placebo and historical controls) on time to liver transplant or death (all-cause) (see [Section 13.1.2.1](#)). Similar statistical methodology as specified above in [Section 13.1.8](#) for supportive analyses will be utilized.

The propensity score quintile will be then be used as the stratification factor in the stratified log rank test to compare groups. KM estimates of the distribution of the time-to-event will be tabulated and graphed by treatment group. The tabulation will include the KM estimate of the medians and corresponding 95% CIs if the medians can be estimated. The number and percent of subjects censored and with events will be presented. The hazard ratio and 95% CI will be determined based on a Cox regression model stratified by randomization strata to estimate the magnitude of the effect.

In addition, the outcome events specified above in Section 13.1.8 will also be evaluated to compare all subjects in OCA population to all control subjects (randomized placebo and historical controls).

Sensitivity analyses will be conducted limiting to the separate individual historical control databases, ie, UK-PBC Group and Global PBC Study Group. To evaluate the robustness of the propensity score estimations, additional algorithms and factors may be considered.

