9.4. Randomization and Blinding

This study will be conducted in a double-blind, placebo-controlled manner. Allocation to 1 of 2 treatment groups (OCA or placebo) will occur on a 1:1 ratio across sites and will be stratified by UDCA treatment (yes/no) and mean baseline bilirubin categories ($>ULN/\leq ULN$), as specified by the central laboratory. The randomization will be based on a predefined randomization code (generated by the Sponsor or designee) using an interactive web response system (IWRS), which the Sponsor intends will serve as a computer-based subject registration system at Screening and Day 0. The IWRS will serve as an investigational product inventory and management system and may be integrated with the study database.

The Investigator or designee will be required to register the subject in the IWRS and may be prompted to provide subject data necessary to properly randomize and allocate the subject to treatment. A randomization number will be assigned (refer to Section 9.5.2, below) and investigational product dispensing information (ie, bottle number[s]) will be provided.

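### Sections 13.1.8 and 13.1.9 test OCA against controls within propensity-score quintiles but take the hazard ratio from a Cox model stratified by randomization strata, which leaves the estimate open to residual confounding

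*Protocol*

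**What the plan says.** Section 13.1.8 (Supportive Analysis) compares randomized OCA subjects with patients from two observational databases. It estimates a propensity score by logistic regression and cuts it into quintiles. For the test it says: "The propensity score quintile will be then be used as the stratification factor in the stratified log rank test to compare randomized OCA-treated subjects". For the effect size in the same comparison, the hazard ratio and 95% CI are "determined based on a Cox regression model stratified by randomization strata to estimate the magnitude of the effect". The propensity score does not appear in that sentence.

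Section 13.1.9 (Alternative Primary Analysis) applies if the sample size re-estimation leads to open-label enrolment. It invokes "Similar statistical methodology as specified above in" Section 13.1.8 and repeats the same pair: quintile strata for the log rank test, randomization strata for the Cox model. There the OCA group includes open-label subjects, and the control group pools randomized placebo subjects with historical controls.

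Section 9.4 defines the randomization strata: allocation is "stratified by UDCA treatment (yes/no) and mean baseline bilirubin categories", that is, two binary factors.

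On the adjustment needed for a historical comparison, Section 13.1.8 says "it has to be done considering a full range of covariates across which the treatment and historical controls might differ".

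**The concern.** The test and the estimate for one comparison rest on different adjustments. The Cox sentence is the one used in Section 13.1.3 for OCA versus placebo. It is right there, because both arms were randomized within those strata. Carried into a comparison with patients who were never randomized, it no longer fits.

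At stake is the number most readers will quote. The p-value would be adjusted for the whole propensity model, while the hazard ratio and its interval would not. The two could differ in apparent strength or even disagree on whether the null is excluded. The plan's own reason for using a propensity score would not be carried into the effect size.

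**Working it through.** **1. Plan figure.** The plan gives no figure for the historical comparison. Its 121 events belong to the randomized comparison and reproduce by Schoenfeld's formula: 4 × (1.960 + 0.842)² / (ln 0.60)² = 31.4 / 0.261 ≈ 120.3, rounded up to 121. Nothing here disputes that.

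**2. Literal reading.** A stratified Cox model learns about treatment only from risk sets in which both groups are present within a stratum.
- Section 13.1.8: every OCA subject has a randomization stratum and no historical control has one. They share no stratum, so the model carries no information on their contrast.
- Section 13.1.9: randomized OCA and randomized placebo subjects have strata; historical controls and later open-label OCA subjects do not. If those without a stratum drop out, the hazard ratio describes only the randomized subset, while the log rank test describes the pooled groups.

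**3. Charitable reading.** Strata are derived for everyone from UDCA (yes/no) and bilirubin (>ULN/≤ULN), giving at most 2 × 2 = 4 cells. All other propensity covariates are left out of the estimate. Section 13.1.2 of Amendment 1 assumed 95% of subjects on UDCA, so on that assumption the UDCA factor separates few trial subjects.

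**4. How much this could matter: a covariate outside the strata.** All inputs are assumptions except the arm size, 350 / 2 = 175.
- 175 OCA subjects, 1500 controls, 400 replicates per row, censoring uniform on 6 to 8 years.
- Hazard = (ln 2 / 8) × exp(ln HR × OCA + γX + 0.5 × bilirubin − 0.3 × UDCA − 0.2), with γ = ln 1.5 or ln 2.
- X is prognostic and lies outside the randomization strata; its mean is lower (healthier) in OCA by the stated shift.
- UDCA use is 93% in OCA and 85% in controls; raised bilirubin is 70% and 60%.
- The propensity model contains X, UDCA and bilirubin.

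| True HR | Shift in X (SD) | HR per SD of X | Cox, randomization strata | Cox, propensity quintiles |
|---|---|---|---|---|
| 1.00 | 0 | 1.5 | 0.998 | 1.000 |
| 1.00 | 0 | 2.0 | 0.998 | 1.006 |
| 1.00 | 0.3 | 1.5 | 0.884 | 0.985 |
| 1.00 | 0.3 | 2.0 | 0.820 | 0.973 |
| 1.00 | 0.5 | 1.5 | 0.824 | 0.983 |
| 1.00 | 0.5 | 2.0 | 0.736 | 0.972 |
| 0.60 | 0 | 1.5 | 0.612 | 0.612 |
| 0.60 | 0 | 2.0 | 0.621 | 0.616 |
| 0.60 | 0.3 | 1.5 | 0.538 | 0.598 |
| 0.60 | 0.3 | 2.0 | 0.525 | 0.614 |
| 0.60 | 0.5 | 1.5 | 0.500 | 0.595 |
| 0.60 | 0.5 | 2.0 | 0.454 | 0.592 |

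In the four rows with a true HR of 1.00 and a non-zero shift, the Cox 95% interval excluded 1 in 13%, 31.5%, 29% and 62% of replicates with randomization strata, and in 3% to 4.5% with quintiles.

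**5. A confounder partly captured by the strata.** Assumptions: 175 OCA subjects, 500 to 2000 controls, one confounder with log-hazard −0.5 per SD, OCA healthier by 0.5 to 1.0 SD, and a noisy dichotomy of that confounder standing in for the randomization strata. With a true HR of 1.00, the dichotomy strata gave 0.71 to 0.85 and propensity quintiles gave 0.94 to 0.98.

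**6. How much confounding the reconstructed strata remove.** In that setting with 500 controls and a dichotomy noise of 1 SD, the unadjusted HR was about 0.79 (shift 0.5 SD) and 0.63 (shift 1.0 SD); with dichotomy strata it was 0.85 and 0.73. The share of log-HR bias remaining is ln 0.85 / ln 0.79 = 0.163 / 0.236 = 0.69, and ln 0.73 / ln 0.63 = 0.315 / 0.462 = 0.68. With a less noisy dichotomy, 26% to 51% remained.

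**The case against.** Several points on the other side stand.

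- **Strata can be derived.** Sections 13.1.1.1 and 13.1.8 say the databases hold liver biochemistry and UDCA treatment. A reader might infer from the literal text that the model cannot be fitted, or that the hazard ratio carries nearly all the confounding. The documents support neither: derived strata would remove part of it (step 6), and the exact fault is residual confounding by the remaining covariates.
- **The imbalance is assumed.** Section 13.1.1 requires historical controls with demonstrated comparability, and Section 13.1.8 adds "Historical controls will be chosen based on the same inclusion/exclusion criteria where possible". Both reduce imbalance, and with none there is no bias. They do not settle the matter, because the eligibility match is qualified and the plan itself still calls for a propensity score.
- **The planned test is the log rank test.** A reader might take the 13% to 62% as an inflated type I error for the trial. It is not: those rates describe the Cox interval. The stated test uses quintile strata.
- **The reach is limited.** Section 5.5.2.2 makes the historical comparison supportive of the placebo comparison. Section 13.1.9 applies only if, after 4 years of accrual, at least 2 more years are needed; Section 13.1.2.1 then requires any change to treatment allocation to be documented in a protocol amendment.
- **The SAP could correct it.** The protocol leaves only the covariates to that document: "The covariates and factors collected in the historical databases will be specified in the SAP". The Cox stratification is fixed in the protocol, so this is a wrong statement and not an omission.

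The planned sensitivity analyses do not cover the point. They vary the database and the propensity algorithm, not the Cox stratification.

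**Conclusion.** The point holds as a mismatch that should be fixed. As written, the hazard ratio for OCA against historical controls either has no usable strata or adjusts for two dichotomized factors only, which contradicts the plan's own case for broad covariate adjustment.

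Its numerical effect in this trial is unknown in size and direction. Across the assumed scenarios with a true hazard ratio of 1.00 and OCA healthier by 0.3 to 1.0 SD, the estimate fell to about 0.71 to 0.88, against 0.94 to 0.99 with quintile strata. An imbalance the other way would bias against OCA.

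A reader might infer that the trial's main result is compromised. It is not: the randomized OCA versus placebo analysis in Section 13.1.3 uses the right strata. The consequence is greatest if Section 13.1.9 is triggered. Both sentences also stand in the original protocol, but Amendment 1.1 is shown only up to Section 9.7.9, so a later correction cannot be excluded.

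**What to change.** In Sections 13.1.8 and 13.1.9, state that the Cox model is stratified by propensity-score quintile, using the same strata as the log rank test. Keep randomization strata for the randomized OCA versus placebo analyses only. First check whether Section 13 of Amendment 1.1 already does this.

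The cost is two sentences in the protocol, mirrored in the SAP; no data collection or patient burden changes. Making the change before the propensity scores are determined and treatment is unblinded, the point by which Section 13 requires the SAP to be approved, avoids a post hoc choice of estimator.

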13.1.9. Alternative Primary Analysis

Based on sample size re-estimations, it may be determined that subjects will be enrolled to receive open-label OCA from that point forward, and the new primary efficacy analysis will become the comparison of all subjects in OCA population, to all control subjects (randomized placebo and historical controls) on time to liver transplant or death (all-cause) (see [Section 13.1.2.1](#)). Similar statistical methodology as specified above in [Section 13.1.8](#) for supportive analyses will be utilized.

The propensity score quintile will be then be used as the stratification factor in the stratified log rank test to compare groups. KM estimates of the distribution of the time-to-event will be tabulated and graphed by treatment group. The tabulation will include the KM estimate of the medians and corresponding 95% CIs if the medians can be estimated. The number and percent of subjects censored and with events will be presented. The hazard ratio and 95% CI will be determined based on a Cox regression model stratified by randomization strata to estimate the magnitude of the effect.

In addition, the outcome events specified above in Section 13.1.8 will also be evaluated to compare all subjects in OCA population to all control subjects (randomized placebo and historical controls).

Sensitivity analyses will be conducted limiting to the separate individual historical control databases, ie, UK-PBC Group and Global PBC Study Group. To evaluate the robustness of the propensity score estimations, additional algorithms and factors may be considered.

13.1.10. Handling of Dropouts or Missing Data

Subjects who discontinue investigational product are expected to continue in the study until study termination.

Missing data will be assumed to be missing at random. In order to determine the effect of missing data on the analysis, efficacy endpoints will be analyzed using different methods of imputation as described below.

13.1.10.1. Time to Event Endpoints

For the time to event analyses, subjects who do not experience an event will be censored at the time of their last contact. Subjects with no data after randomization will be considered to have an event on Day 1 (first day of investigational product dosing).

For analyses of the percentage of subjects with an event, subjects with no data after randomization will be considered to have an event.

All time to event endpoints include only adjudicated events. Sensitivity analyses may consider all events regardless of adjudication. Events with discrepant adjudication will be analyzed using both results.

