13.1. Efficacy Analysis

13.1.1. Analysis Populations

The following subject populations will be evaluated and used for presentation and analysis of the data:

- The Randomized Population will include all randomized subjects.
- The Intent-to-Treat (ITT) Population will include all randomized subjects who receive any amount of investigational product (OCA or placebo). The ITT Population will be the primary population used for efficacy analyses. Treatment assignment will be based on the randomized treatment.
- The Safety Population will include all subjects who received any amount of investigational product (placebo or OCA). The Safety Population will be the primary population used for safety analyses. Treatment assignment will be based on the treatment actually received.
- The PK population will include all OCA subjects who have at least one confirmed fasted analyzable sample. Subjects must have been fasting for approximately 8 hours prior to the visit and must not have any major protocol deviations that potentially affect exposure levels. The PK population will be used for OCA PK analyses.
- The Overall Historical Control Population will include subjects from the United Kingdom (UK) -PBC Group and Global PBC Study Group databases with demonstrated comparability to randomized subjects in this clinical study (747-302) with respect to both subject characteristics and disease progression.
- The UK-PBC Historical Control Population will include subjects from the UK-PBC Group databases with demonstrated comparability to randomized subjects in this clinical study (747-302) with respect to both subject characteristics and disease progression.
- The Global PBC Historical Control Population will include subjects from the Global PBC Study Group database with demonstrated comparability to randomized subjects in this clinical study (747-302) with respect to both subject characteristics and disease progression.

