13.1.3. Primary Efficacy Analysis

The primary efficacy endpoint will be the time to first occurrence of one of the following post-randomization:

- Death (all-cause)
- Liver transplant
- MELD score ≥ 15
- Hospitalization (as defined by a stay of 24 hours or greater) for new onset or recurrence of:
 - Variceal bleed
 - Encephalopathy (as defined by a West Haven score of ≥ 2)
 - Spontaneous bacterial peritonitis (confirmed by diagnostic paracentesis)
- Uncontrolled ascites (diuretic resistant ascites requiring therapeutic paracentesis at a frequency of at least twice in a month).
- Hepatocellular carcinoma confirmed by 2 complimentary imaging modalities.

The primary efficacy analysis will compare randomized OCA to randomized placebo with respect to the primary efficacy endpoint using the ITT population. Only adjudicated events will be included in analyses. The 2 treatment groups will be compared using the log rank test stratified by the randomization stratification factor. Kaplan-Meier (KM) estimates of the distribution of the time-to-event will be tabulated and graphed by treatment group. The tabulation will include the KM estimate of the medians and corresponding 95% confidence intervals (CIs), if the medians can be estimated. The number and percent of subjects censored and with events will be presented. The hazard ratio and 95% CI will be determined based on a Cox regression model stratified by randomization strata to estimate the magnitude of the effect.

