13.1.4. Key Secondary Efficacy Analyses

The key secondary efficacy endpoints will compare OCA to placebo on the following:

- Time to first occurrence of MELD score ≥ 15
- Time to liver transplant or death (all-cause)
- Change from Baseline in total bilirubin at end of study
- Change from Baseline in ALP at end of study

The key secondary efficacy analyses will compare randomized OCA to randomized placebo in ITT population with respect to the key secondary efficacy endpoints. Only adjudicated events will be included in time-to-event analyses. The comparison (hypothesis testing) will be

conducted as specified in [Section 13.1.11](#) in a sequential closed testing gate-keeping procedure, provided that the primary efficacy endpoint comparison is statistically significant in favor of the OCA treatment group. If the primary comparison is not statistically significant then comparison of the secondary endpoints will be considered as descriptive and exploratory. This procedure controls the study-wise type I error.

The 2 treatment groups will be compared using the same methodology as specified for the primary efficacy analysis ([Section 13.1.3](#)).

Analyses of change from Baseline to end of study in ALP and total bilirubin will be compared between treatment groups using analysis of covariance (ANCOVA) with change from Baseline as the dependent variable including treatment group and randomization stratification factor as fixed effects and the Baseline values as a covariate. The same analysis will be carried out using percentage change from Baseline as the dependent variable.

Descriptive statistics of the laboratory values will be summarized by treatment group. The results, change from Baseline, and percentage change from Baseline values as well as estimates of least-square means, standard errors, and 95% CIs will be presented by treatment group. Estimates of the mean difference between treatment groups, the standard error of the difference, and 95% CI of the difference will be presented.

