13.4. Adjudication Committee

All potential endpoint events will be reviewed by an adjudication committee before inclusion in the any analysis. The adjudication of potential clinical endpoint events will include, but is not limited to: available hospital reports, histology, discharge summaries, and death certificates. The assessment of events will be conducted in compliance with the protocol, study-specific procedures, manuals, Good Clinical Practice (GCP), and all other applicable regulatory requirements, including the archiving of essential documents. A separate adjudication committee charter will document the entire data flow and process from committee membership, the reporting of events by the study site, reporting of the final assessment, supply of source documentation to the committee, the review of the events by the committee, and the working procedures of the committee. The adjudication committee members will be independent hepatologists not involved in the study as investigators, DSMC members, or consultants. All adjudication committee members will remain blinded to treatment group throughout the study.

In addition to potential clinical endpoint events, cardiovascular events will also be adjudicated. The adjudication of these events will be handled separately from the adjudication of events for assessment of the primary endpoint in this study and will be described separately.

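### Section 13.1.10.1 counts subjects with no post-randomization data as Day 1 events, against the protocol's own adjudicated-events-only rule; the reach is probably small, but the rule should become censoring

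*Protocol*

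**What the plan says.** Section 13.1.10.1 first gives the ordinary rule: "subjects who do not experience an event will be censored at the time of their last contact". The next sentence makes an exception: "Subjects with no data after randomization will be considered to have an event on Day 1 (first day of investigational product dosing". Both belong to the general handling of time-to-event endpoints, and neither is presented as a sensitivity analysis. The same section goes on: "All time to event endpoints include only adjudicated events".

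Three other places bear on this:

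- Section 13.1.3, on the primary analysis: "Only adjudicated events will be included in analyses".
- Section 13.4: "All potential endpoint events will be reviewed by an adjudication committee before inclusion in the any analysis".
- Section 13.1.10, on missing data in general: "Missing data will be assumed to be missing at random".

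The rule reaches past the primary endpoint. For the key secondary endpoints Section 13.1.4 says: "The 2 treatment groups will be compared using the same methodology as specified for the primary efficacy analysis". Two of these, MELD score of at least 15 and transplant or all-cause death, are time-to-event endpoints in the confirmatory hierarchy.

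The primary analysis set is defined in Section 13.1.1: "The Intent-to-Treat (ITT) Population will include all randomized subjects who receive any amount of investigational product (OCA or placebo". Sections 9.1 and 9.7.1 put the first dose on the day after randomization.

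This is the Amendment 1 text, and the original protocol has the same rule. The available copy of version 1.1 stops before its Section 13, so the wording there cannot be confirmed.

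**The concern.** An event created because nothing is known about a subject cannot have been reviewed by the adjudication committee. Two statisticians following this text could therefore run different primary tests: one adds the Day 1 events, and the other excludes them as unadjudicated. A confirmatory analysis should not be open in that way.

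The rule also gives a poor answer whenever it applies. A silent subject is entered as having reached the composite endpoint on Day 1, and again as having reached MELD of at least 15, and again as transplanted or dead. The imputed event falls when the risk set is at its largest. If such subjects are equally common in both arms, they dilute the treatment effect. If they are not, the test moves toward the arm with fewer of them. Assuming the worst for every missing subject is therefore not the same as being conservative about OCA.

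**Working it through.** **Inputs.** Section 13.1.2: hazard ratio 0.60, 1:1 allocation, 2-sided 5% log-rank test, 121 events, 80% power, about 350 subjects, 2 years of accrual and 6 of follow-up, placebo event-free proportion 0.5 at 8 years. The number of no-data subjects is not in the protocol; the values of k below are assumptions.

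**The plan's own figure.** Schoenfeld's formula gives 4(1.960 + 0.842)²/(ln 0.60)² = 120.3, so 121 events. Expected |Z| at 121 events is 0.511 × √121/2 = 2.81, and power is Φ(2.81 − 1.96) = 0.802. The stated figures reproduce.

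**Which total to use.** Sections 7.1 and 13.1.2.1 stop the study on adjudicated events. Imputed events are not adjudicated, so they come on top of 121 real events.

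**Approximation.** Each Day 1 event adds about ±0.5 to the log-rank score, and information is one quarter of the events:

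- U = ln(HR) × 121/4 + (k_OCA − k/2)
- V = (121 + k)/4
- Z = U/√V, and the estimated HR is exp(U/V)

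**Balanced split (dilution).** |Z| = 2.81 × √(121/(121 + k)). Power is 0.796 for k = 2, 0.783 for k = 6, 0.770 for k = 10 and 0.758 for k = 14. For k = 10, U = −15.45 and V = 32.75, so the estimated HR is 0.62.

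**Four subjects, all in one arm.** The shift in Z is 2/√(125/4) = 0.358.

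- All on placebo, no true effect: the chance of a false win for OCA is Φ(−1.96 + 0.358) = 0.055, against 0.025.
- All on OCA, true HR 0.60: power is Φ(2.81 × √(121/125) − 0.358 − 1.96) = Φ(0.446) = 0.67.

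**Ten subjects, seven on OCA and three on placebo.** U = −15.45 + 2 = −13.45 and V = 32.75, so Z = −2.35 and the estimated HR is 0.66.

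**No such subjects.** No effect.

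**Simulation check.** 350 subjects, exponential times, 2-year accrual, cut at 121 real events, 4,000 runs per scenario, unstratified log-rank test (the planned test is stratified):

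| No-data subjects | Day 1 event rule |
|---|---|
| 4 placebo, 0 OCA | false win 0.055 |
| 0 placebo, 4 OCA | power 0.67 |
| 7 placebo, 0 OCA | false win 0.087 |
| 0 placebo, 7 OCA | power 0.54 |

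With the same subjects censored at Day 1, simulated power stayed at 0.79–0.81 and the false-win rate at 0.021–0.027 in every scenario run.

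**The case against.** The strongest objection is that the rule may reach almost nobody. The ITT set requires a dose, the first dose comes the day after randomization, and showing that a dose was taken normally needs some later information. A subject with nothing after randomization can rarely be shown to belong to the primary set. The Month 1 and Month 2 telephone contacts, and the telephone or record-review options after partial withdrawal, shrink the group further. This stands. A reader might take a few percent of all 350 subjects as affected, but nothing in the protocol supports such a figure.

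Second, a reader might infer that imputed events use up part of the 121. They do not: the stopping rule is already written in adjudicated events.

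Third, a reader might infer that the rule manufactures a benefit for OCA. That needs a placebo-heavy imbalance, which no passage suggests. The error rates above are conditional on the split shown. If early loss is unrelated to treatment, four subjects all fall in the same arm with probability 2 × 0.5⁴ = 0.125, in either direction.

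Fourth, Section 13.1.10 also announces several imputation methods to gauge the effect of missing data, so the clash with missing at random is a tension rather than a flat contradiction. That is fair, but Section 13.1.10.1 offers no alternative for these subjects and does not call the Day 1 event a sensitivity rule. Where this section and Section 13.1.10.2 mean a sensitivity analysis, they say so.

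None of this removes the conflict with the adjudication requirement.

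**Conclusion.** The point holds as a badly fixed, self-contradicting rule in the confirmatory analysis, not as a demonstrated bias. The conflict with the adjudicated-only requirement follows from the text alone and needs no assumption.

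The size depends on a count the protocol does not give and which the dosed-only ITT definition probably keeps small, possibly at zero. The direction is not fixed either. The figures for four and ten subjects show sensitivity to a handful of cases; they do not predict what will happen. The stronger reading, that the primary test is already contaminated, is not supported.

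The rule still deserves correction. For a subject who vanishes after Day 0, whether a dose was taken may be unknowable, so a later decision on ITT membership could add an event to the primary test.

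**What to change.** In Section 13.1.10.1, replace the Day 1 event sentence with one that censors subjects with no post-randomization data at randomization/Day 1 in the primary and all other time-to-event analyses. State that only adjudicated events enter the test, as already required for the 121-event stop. Keep no-data-equals-event only as a labeled sensitivity analysis. If version 1.1 repeats the rule in its Section 13, make the same change there and carry it into the SAP before unblinding.

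The cost is one sentence: no extra subjects, visits or procedures. Moving the primary analysis to the Randomized Population is a separate question and not part of this change; a no-data subject censored at Day 1 adds nothing to the log-rank test in either population.
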